7. PRIVACY AND CONFIDENTIALITY

Data and Safety Monitoring Plan

Data Entry Methods

Our general policy for data management is that research assistants copy all data files and these files are brought to [name] on a weekly basis. Data forms and accompanying narrative summaries will undergo a systematic and rigorous editing process before they are keyed into the database. The research assistants routinely evaluate the data and discuss any problems and questions with the study staff and [name] at regular weekly team meetings. Accuracy of data entry will be ensured by a standard double-entry procedure. Data management formal reports on record status across the three following domains will be employed: entered, verified, and edited. These reports of data records will be evaluated one time a month during the final team meeting of the month. To help ensure data protection, backup copies, automatically generated by our computer systems, will be available. Additionally, our hard copy record systems, as described previously, will be maintained in fire-resistant locked cabinets.

This study will utilize a web page-internet data collection and management system used in previous work. All data for the current study including demographic information, diagnoses, laboratory values, medication counts, and participant and clinician rated measures will be directly entered into an electronic case report form (eCRF). The eCRF will be entered into a dedicated computer at the University of Texas maintained by [name] in his capacity as chief study data manager.

The eCRF will consist of a series of separate web pages for study personnel and participants. A series of passwords will be programmed to ensure that participants are unable to access pages reserved for study personnel. The eCRF will be constructed so that all requested information must be entered into each page in the fields provided, or the system will not permit access to the next page. The system is designed so that only completed eCRFs can be transmitted. If information for a field is either not available or not applicable, the system will require that it be documented as such in

Research Proposal

the eCRF. Field parameters will be specified such that suspect values are either disallowed or flagged for the immediate attention of the study directors and Principal Investigators.

At each visit a hard copy of the eCRF will be printed and promptly reviewed, signed, and dated by the investigator for clinician rated measures and by the participant for participant rated measures. A print out of the data will then be made, authenticated (with signature and date) by the investigator and participant and kept in the participant's study file.

Some study data (eCRF) will be collected and managed using Qualtrics and REDCap. Qualtrics and REDCap are high-end web survey tools that have been used in experimental research and is designed in a way that ensures the security of data transmission and protection. Qualtrics and REDCap offers Transport Layer Security (TLS) encryption (HTTPS) and survey security options like password protection and HTTP referrer checking. Qualtrics and REDCap are HIPAA compliant, and servers are stored in a tier one data storage facility that includes adequate security measures.

CONFIDENTIALITY OF THE DATA OR SAMPLES

a. Describe how data or samples (i.e., blood, saliva, tissue, etc.) will be collected.

- Saliva samples will be collected using salivettes (Sarstedt, Rommelsdorf, Germany), which are plastic vials with cotton dental rolls inside.

b. Describe how the data or samples will be securely stored and how you will achieve this.

- Once the samples are collected, they will be frozen and stored (-80 degrees C) for future processing. To extract saliva, the samples will be centrifuged at 4 degrees C for 5 minutes at 2000 xg. They will be assayed with an enzyme immunoassay at Salimetrics, LLC, located in State College, PA, using a commercial kit (Diagnostic Products Corporation, Los Angeles, CA).

c. Provide the length of time the data or samples will be kept.

- Salimetrics, LLC will immediately dispose of the cotinine samples once the information needed is collected.

d. Describe whether data or samples will be kept confidential (i.e., data can potentially be linked to participants) or anonymous (i.e., impossible to link data and participants). You must include if the data or samples will be shared by other researchers for research purposes not detailed in this study.

- The results of cotinine analyses will be kept confidential and will not be returned to participants in this study. Further, tubes will be identified by participant identification numbers only. Staff processing the cotinine samples will not have access to any identifying information of the participants.

e. If the data or samples will be destroyed, describe when and how the destruction will occur.

- Salimetrics, LLC will take all precautions and dispose of the cotinine samples in a biohazard disposal.

8. COMPENSATION

Participants will be paid \$25 for the baseline visit, \$10 for weeks 1, 2, 4, 5, 6, and 7, \$15 for week 3, and \$20

Research Proposal

each follow-up (Weeks 9, 13, 15, 21, 29). Thus, participants can receive up to \$200 for their participation in the study. These payments are not contingent upon smoking status at the time of assessment or follow-up. We feel this amount is appropriate in order to assure that all participants involved with the study have the means to attend assessment visits, thus aiding our goal of evaluating treatment efficacy at various time points.

Enhancing Panic and Smoking Reduction Treatment with D-Cycloserine

NCT01944423

Last updated: 6/7/2017

Data Analysis.

Overview. First, we will assess the equivalence of the treatment groups on key baseline variables (demographics, smoking characteristics, psychological variables); variables on which the groups differ will be used as a covariate in final analyses. We will then examine missing data patterns, dropout rates (see below), and distributional properties of measures and use transformations to improve distributions when necessary.

Following recommendations of the Society for Research on Nicotine and Tobacco (Hall et al., 2001), the effects of treatment on PPA will be examined using Generalized Linear Mixed Models (GLMM), employing the logistic linking function. In our GLMM analyses, the repeated measures will be nested within individuals, which will be nested within their treatment cohort, thereby appropriately accounting for correlated scores within the small cohorts. Our GLMM analysis will model outcome as a curvilinear (quadratic) or exponential function of time (based on AIC and BIC) since PPA is expected to decrease rapidly at first and then level off over time. Using this model, one can test differences between treatment groups by including treatment condition as an “individual level” predictor of rate of decrease in PPA over time. We can also examine treatment group differences in PPA at any assessment point. Multi-level models (MLMs) similar to the GLMM models will be used to test treatment differences in continuous outcomes (the psychological variables: withdrawal symptoms, negative affect, panic severity, distress intolerance, and anxiety sensitivity). All models will include relevant control variables (e.g., gender, education, nicotine dependence, etc.). We will also run a Cox proportional hazards survival analysis predicting risk of lapsing or relapsing to smoking and compare the two conditions on these outcomes.

Tests of specific aims. Aim 1a: Treatment differences in slopes will indicate different rates of decrease in PPA. To determine whether there are treatment differences in PPA at any particular time point (e.g., week 24), we will center the “Time” variable in the GLMM model at that time point (Singer & Willett, 2003). **Aim 1b:** Cox proportional hazard models will be used to test for differences between treatments in relative risk of lapse and relapse, and in time to first lapse and to relapse. **Aim 2a:** The same analyses in Aim 1a will be used in MLMs to test for treatment differences in the psychological outcomes (withdrawal symptoms, negative affect, panic severity, distress intolerance, anxiety sensitivity). **Aim 3a:** The “a” paths in our mediation model (see Figure 1 in Specific Aims) will be calculated as in Aim 2a. Because we expect the “a” paths to be moderated, separate analyses will be conducted to calculate the “a” paths for each treatment condition (Tein, Sandler, MacKinnon, & Wolchik, 2004). The “c” path will be calculated as in Aim 1a. **Aim 3b:** The “b” paths in our mediation model will be the regression coefficients for the mediators when all the mediators are simultaneously added to the GLMM equation predicting PPA used in Aim 1a. **Aim 3c.** Tests of the mediated pathways will be conducted separately for each treatment condition (due to moderated mediation [Tein et al., 2004]). Significance of mediated pathways will be determined using Bayesian bootstrap mediation analysis (Yuan & MacKinnon, 2009).

Missing Data. Following Hall et al. (2001) and Enders (2011), we will use pattern mixture modeling to assess the effect of missing data. We will rerun our analyses coding for various missing data patterns (no missing data, sporadic missing, dropouts, etc.) to determine both if missingness impacts our findings and how the differences between PSRT+DCS and PSRT+PBO depend on the missing data pattern.

Power Analysis. Because we will have a sample size of 80, this application is not powered to detect small differences between treatment conditions. However, consistent with the aims of a Stage IB study, our primary goal is determining 1) the feasibility of the new intervention and 2) whether a Stage II study is warranted. Below we estimate (for the lowest powered analyses) the effect sizes (ESs) that we will be able to detect as statistically significant with 80% power.

Aim 1a: GLMM model comparing PPA in the PSRT+DCS condition vs. the PSRT+PBO condition. We performed a Monte Carlo study to calculate the minimum PSRT+DCS PPA rate detectable by our analysis. Our assumptions were: an average of 5 assessments per participant (71% of the post quit date assessments) ([name] et al., 2008) and a 27% PPA in PSRT+PBO at the last follow-up (Piper et al., 2010). We examined numerous PSRT+DCS PPA rates to determine the lowest rate detectable by our analysis, performing 1000 simulations for each PPA rate. The results indicated that we would have .80 power to detect a significant treatment effect if the PPA rate in PSRT+DCS at the follow-up was 43% or greater. This difference – i.e., 43% vs. 27% - is equivalent to a Cohen's ω effect size (the effect size measure for proportions) of .17, between a small (.10) and medium (.30) ω effect size (Cohen, 1988). Thus, we have sufficient power to detect a smaller than medium effect.

Aim 3: Moderated Mediation of changes in PPA. The first step in our moderated mediation power analysis was to determine the power to detect moderation of the “a” path (see Figure 1. Using the MLM power analysis program PinT 2.12 (Snijders & Bosker, 1993) to calculate our power to detect moderation of path “a”, we found that we had over .95 power to detect a medium effect size ($d = .50$) for moderation of the “a” path. Next we calculated the power to detect longitudinal mediation for each treatment group, over time. For this analysis, path “a” was the slope of change in the mediator over time, and path “b” was the relation between the mediator and the outcome over time. We performed a Monte Carlo study to calculate the power for a bootstrap mediation analysis. We assumed that the effect sizes for the “a” paths (the change in the mediators over time) would be large ($d > .80$; see 3C.2a), the effect size for the “b” paths would be medium, and the PPA rates were assumed to be those found in Aim 1a (27% for PSRT+PBO and 43% for PSRT+DCS). The Monte Carlo study consisted of 400 samples, for each of which we performed a bootstrap mediation analysis each consisting of 1000 resamples. Results indicated that we would have at least .81 power to detect a mediated effect.

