Our study consists of three aims: to compare, in a randomized clinical trial, (1) the effects of PSRT+DCS versus PSRT+PBO on smoking cessation outcomes and (2) the effect of PSRT+DCS vs. PSRT+PBO on the frequency and intensity of panic attacks, withdrawal symptoms, negative affect, anxiety sensitivity, and distress intolerance; and (3) to explore the

Research Proposal

mechanisms by which PSRT+DCS improves smoking cessation outcomes. We hypothesize that individuals in the PSRT+DCS condition will evidence superior smoking cessation outcomes (i.e., longer time to first smoking lapse and relapse and lower PPA) and reduced anxiety and panic symptomatology compared to those in the PSRT+PBO condition.

To achieve our aims, adult smokers with panic attacks from the Austin community will be randomly assigned to either: (1) PSRT+DCS or (2) PSRT+PBO. Primary outcome measures will be point prevalence abstinence (PPA), time to first smoking lapse, and time to smoking relapse. Proposed mediators include panic attacks, distress intolerance, anxiety sensitivity, nicotine withdrawal symptoms, and negative affect. These variables will be assessed at baseline, weekly during the treatment phase, and at 2, 4, 8, 10, 16, and 24 weeks after quit date.

The proposed study represents a crucial and important stage in translating basic research to strategies for treating nicotine dependence. The investigation addresses an important public health issue by testing an integrated intervention - informed by basic research - that may lead to a more effective and efficient treatment for at-risk smokers while simultaneously isolating explanatory mechanisms. The expected findings should: (1) guide advances in the theoretical conceptualization of the mechanisms involved in panic- and anxiety-smoking relations; and (2) provide initial effect size data for the addition of DCS to an integrated psychosocial/behavioral and pharmacological smoking cessation intervention for smokers with panic attacks, and thus provide the necessary data for a large-scale follow-up trial.

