The consent form will be sent to participants via REDCap before the appointment so that they have time to read through the form and give their informed consent. Upon arrival, if the participant has not signed the consent form, they will receive an informed consent form explaining the details of the study, potential benefits and risks of participation, and the procedures they will undergo if they choose to participate. After reading the informed consent document, a study coordinator will discuss these issues with the potential participant and will answer any questions he or she may have about the study and participation. If the individual chooses to sign the informed consent, he or she will have their blood pressure, heart rate, and CO₂ measured. Those who have readings outside of the safe range (ranges are provided by our study physician: 85mmHg < Systolic BP < 160mmHg and 55mmHg < Diastolic BP < 100mmHg) will have their measurements sent to our study physician for further safety assessments. If the physician deems it is unsafe for the participant to take the study medication, they will be notified, thanked for their time, and dropped from the study. All participants will continue with the rest of the baseline visit which includes introduction to the research study, goals of the treatment, explanation of data collection documents, and assignments including surveys to be completed before coming to the lab. Participants will also be asked to provide contact information of two significant others we can reach out to if we lose contact with them. If we need to contact these significant others, we will let them know the participant gave us their information, if they can provide us with the participant's new contact information (if it has changed, and/or leave them a message asking to contact us.

Randomization

The project Biostatistician, [name], will oversee the randomization to either PSRT+DCS or PSRT+PBO conditions. Both participants and study personnel will be blind to study condition, and study medication will be labeled by either "A" or "B" by the pharmacy in order to blind the medication administration. A random number generator will be used to assign individuals to either condition. Only [name] will have the information necessary to break the blind. Prior to data analyses, [name] will check the balance of randomization and control for any factors that are imbalanced.

Intervention Modules

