at the University of Texas by a certified phlebotomist and Clinical Pathology Laboratories in Austin will analyze the samples.

Measures of smoking behavior, nicotine dependence, and withdrawal symptoms

Smoking History Questionnaire (SHQ). Smoking history and pattern will be assessed with the SHQ, a 30-item measure that includes items pertaining to smoking rate, age of onset of initiation, years of being a regular smoker, etc. (Brown et al., 2002; [name] et al., 2005). This measure will serve to contextualize the participants' smoking behavior and history at intake.

Fagerström Test for Nicotine Dependence (FTND). The FTND is a 6-item scale designed to assess gradations in tobacco dependence (Heatherton et al., 1991). This measure will serve to quantify nicotine dependence, which will be used as a covariate in the primary analyses.

Nicotine Withdrawal Symptoms. Given its potential relation to outcome, we will monitor withdrawal severity at baseline, weekly throughout treatment and at follow-up assessments, using the Minnesota Withdrawal Scale, a reliable and sensitive 10-item scale (Hughes & Hatsukami, 1986).

Questionnaire of Smoking Urges (QSU). The QSU is a 10-item measure that assesses urges and cravings for cigarettes (Cox et al., 2001). We will monitor craving at baseline, weekly throughout treatment, and at the follow-up assessments. This assessment of urges can be used to evaluate consistency (or lack thereof) with withdrawal symptoms in follow-up tests from the data set.

Smoking Abstinence Expectancies Questionnaire (SAEQ). The SAEQ is a 28-item measure that assesses short-term psychological and physiological consequences to (hypothetically) abstaining from smoking among those that smoke everyday. The measure has 4 internally consistent subscales: Negative Mood, Somatic Symptoms, Harmful Consequences, and Positive Consequences.

Smoking Cessation Self-Efficacy (SE). A participant's confidence that he or she can carry out a behavior such as quitting smoking will be measured at baseline using a well-established 9-item scale developed by Velicer, Diclemente, Rossi, and Prochaska (1990). This instrument includes a subscale regarding confidence in remaining abstinent in negative affect. In previous work, we have successfully used this negative affect subscale for smoking self-efficacy ($\alpha = .85$; [name], Schmidt et al., 2003).

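### The covariate set is not fixed in advance: on top of an open control list, the plan adds any baseline variable on which the randomised groups happen to differ, with no criterion for differing.

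*SAP*

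**What the plan says.** Three statements together determine the covariates.

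- **Imbalance rule.** The SAP's Overview first compares the groups on "key baseline variables (demographics, smoking characteristics, psychological variables"), and then "variables on which the groups differ will be used as a covariate in final analyses". In the protocol (section 4, Randomization) the biostatistician, before the data analyses, "will check the balance of randomization and control for any factors that are imbalanced".
- **Control variables in every model.** The same SAP paragraph says: "All models will include relevant control variables (e.g., gender, education, nicotine dependence, etc".). The list is introduced as an example and ends with an etc.
- **One firm commitment.** Protocol section 5 says of the Fagerström Test for Nicotine Dependence (FTND): "This measure will serve to quantify nicotine dependence, which will be used as a covariate in the primary analyses".

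Neither document gives a test, a threshold or a closed list of variables for the imbalance rule. On allocation, the protocol says: "A random number generator will be used to assign individuals to either condition". It describes no stratification factors.

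**The concern.** Under random allocation, baseline differences between the arms are due to chance. Their size says nothing about which variables predict abstinence, so choosing covariates by imbalance is choosing on the wrong property. Because no criterion for a difference is given and the control list is open, two analysts following this SAP could fit different primary models to the same data and report different treatment estimates.

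There is a second consequence for the continuous outcomes. The baseline value of a psychological scale is a natural candidate for the strongest predictor of its later value, yet the plan does not name it as a control variable. Under the imbalance rule it would enter only when the arms happened to differ on it. The SAP does not say whether baseline is one of the repeated measures in those multi-level models (MLMs).

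**Working it through.** **Inputs from the documents.** N = 80 (SAP, Power Analysis); PPA of 27% and 43% at follow-up (SAP, Aim 1a power); logistic link for PPA (SAP, Overview); control variables gender, education and nicotine dependence.

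**Assumptions, because the documents are silent.** 40 per arm; two-sided .05; a difference means p<.05; independent covariates; the number K of variables examined; the share of outcome variance (R²) that covariates explain.

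**1. The plan's own effect size.** ω = |p1 − p2| / (2√(p̄q̄)) = .16 / (2√(.35 × .65)) = .168, which agrees with the stated .17. On the log odds scale the planned effect is ln[(.43/.57)/(.27/.73)] = 0.71. This point disputes neither figure; they only give a scale.

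**2. How often the rule acts.** P(at least one flagged) = 1 − .95^K.

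| K | P(at least one) | Expected number flagged |
|---|---|---|
| 5 | 23% | 0.25 |
| 10 | 40% | 0.5 |
| 15 | 54% | 0.75 |
| 20 | 64% | 1.0 |

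**3. Cost in power when the named controls carry the prognosis.** Simulation with K = 10, of which three are prognostic and always in the model. A fixed set of those three is compared with the plan as written (the three plus any flagged variable).

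| Outcome | R² | Fixed set | Plan as written |
|---|---|---|---|
| Linear, effect 0.5 SD | .1 | .630 | .620 |
| Linear, effect 0.5 SD | .3 | .733 | .723 |
| Linear, effect 0.5 SD | .5 | .872 | .863 |
| Logistic, 27% vs 43%, one time point | .1 | .338 | .335 |
| Logistic, 27% vs 43%, one time point | .3 | .380 | .376 |

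The loss is about 1 point or less. The logistic powers are for a single time point and are not comparable with the SAP's .80, which belongs to the repeated-measures model.

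**4. Standard errors under the null, plan as written.** Linear: mean standard error against actual SD is .193 vs .192 (R² .3) and .163 vs .163 (R² .5), with type I error .048 to .052 across settings. Logistic: .572 vs .613 (R² .1) and .625 vs .669 (R² .3). The logistic standard error is thus slightly too small, not too large. The fixed set shows the same pattern (.563 vs .603; .614 vs .652), so the imbalance rule is not the cause.

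**5. How far the PPA estimate can move.** Three controls always in the model, 35% abstinent, no treatment effect, one time point, R² .30 split between the controls and a pool of 15 variables. The only thing varied was the undefined threshold (none, .05, .10, .20). The log odds ratio differed across these choices by a median of 0.18, and by 0.48 at the 90th percentile, against the planned effect of 0.71. Each threshold fixed in advance kept type I error near .05. Picking the most favourable threshold after seeing results raised it to about .08. That is a worst case showing the latitude in the text, not a forecast of conduct.

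**6. Psychological outcomes.** Linear outcome, effect 0.5 SD, named controls with R² .05, the outcome's baseline value with R² .2 to .4 sitting in a pool of 12 variables, and baseline not among the modelled repeated measures.

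| | Always adjust for baseline value | Plan as written |
|---|---|---|
| Power | .70 to .83 | .59 to .60 |
| Type I error | .047 to .050 | .037 to .044 |

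**The case against.** The best defence is that the imbalance rule is only an addition. Control variables enter every model whatever the balance, and FTND is promised for the primary analyses. A reader who saw only the imbalance sentence might infer that covariates are chosen by imbalance instead of by prognosis. The documents do not support that.

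A reader might also infer a large power loss and inflated standard errors for PPA. Those follow from an imbalance-only rule with a linear outcome, which is not this plan. Steps 3 and 4 show neither under the plan as written when the named controls carry the prognosis.

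Nor can it be claimed that the person checking balance is the one who holds the treatment code. The names are removed from the protocol's Randomization subsection, so this would be an inference. The check precedes the data analyses, and nothing shows that outcomes steer the selection.

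The 40% to 64% rests on an assumed count and threshold. With five variables it is 23%, and correlated variables would change it. The SAP also describes a Stage IB study that asks about feasibility and whether a Stage II study is warranted, which lowers the stakes of any single test.

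All of this stands and limits the size of the point. It does not answer the core: the rule is written in both documents, has no criterion, and selects on chance.

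**Conclusion.** The point holds as a specification fault with a better method available from data already collected. The covariate set is only partly named, and the rest is settled by chance imbalance under an unstated criterion.

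- **PPA.** The main cost is an estimate that depends on an unstated choice. The power loss is about 1 point or less, provided gender, education and nicotine dependence carry the prognosis. Standard errors are not overstated.
- **Psychological outcomes.** The cost can be real: about 11 to 23 power points in the setting of step 6 (.70 − .59 to .83 − .60), with a mildly conservative test. It applies only if baseline is not already a modelled repeated measure, which the SAP does not say.

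These sizes rest on the assumed K, threshold, R², independent covariates and 1:1 allocation. The logistic runs use one time point, not the full mixed model. The plan should be corrected before unblinding, but the fault does not invalidate the trial.

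**What to change.** 1. Delete the imbalance rule from the SAP's Overview and from the protocol's Randomization subsection, or keep it only as a labelled sensitivity analysis with a stated criterion.
2. Replace the open control list with a closed one, fixed before unblinding: FTND, gender, education and baseline cigarettes per day.
3. In each psychological MLM, account for the outcome's baseline value once: as a covariate if baseline is not one of the modelled repeated measures, otherwise through the repeated-measures model, but not both.
4. Report baseline tables descriptively, without significance tests.

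**Cost.** Both the SAP and the protocol need a wording change. The variables are already collected. Three of the four PPA covariates are already named, so the fixed set adds one. With about 28 abstinent participants expected at the last follow-up (40 × .27 + 40 × .43 = 28), that is a small but real price. For comparison, the present rule would add 0.75 covariates on average with 15 variables at p<.05, chosen by chance.

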In regard to withdrawal symptoms, there is a strong likelihood that most study participants will experience some nicotine withdrawal symptoms, including anxiety, restlessness, anger, irritability, sadness, problems concentrating, appetite change and weight gain, insomnia, and decreased heart rate. Because all participants will use the nicotine patch, this should diminish the overall severity of withdrawal discomfort, although the patch will not necessarily eliminate withdrawal discomfort entirely. Moreover, withdrawal symptoms are usually short-lived, with most symptoms abating within 1-2 weeks. During treatment, research team staff will monitor patients for development of severe psychological problems (e.g., depression) during each of our sessions and follow-up visits. Using the study instruments and clinical interviews, therapists will determine whether treatment or additional treatment for a specific psychological problem is needed and work with the patient to refer them to appropriate service centers.

Regarding the administration of DCS, the prescribing psychiatrist will be [name]., M.P.H., F.A.S.A.M. [name] will review the medical history of patients (for exclusion factors), and will prescribe the three doses of study medication (DCS vs. PBO) to be taken during assessment weeks (weeks 3-5). Patients will be encouraged to call the study physician should they experience any side effects or have any questions regarding the medication.

To deal with the potential risk of loss of privacy (judged to be minimal), we will maintain confidentiality by numerically coding all data, by disguising identifying information, and by keeping all data in locked file drawers. Video recordings will be coded by participant ID and will be deleted after therapist adherence ratings. Participant information will be accessible only to research staff. Identifying information will not be reported.

Functions of the Data and Safety Monitoring Board (DSMB)

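### Aim 2a applies to withdrawal a single time curve chosen for abstinence, and fixes neither the visits nor the time point, so a short-lived post-quit effect can be smoothed away or misread

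*SAP*

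**What the plan says.** In the SAP's Tests of specific aims, Aim 2a covers withdrawal, negative affect, panic severity, distress intolerance and anxiety sensitivity together: "The same analyses in Aim 1a will be used in MLMs to test for treatment differences in the psychological outcomes". The Overview describes the models loosely: "Multi-level models (MLMs) similar to the GLMM models will be used to test treatment differences in continuous outcomes".

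The rule being borrowed has three parts.

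- **Shape (Overview).** "Our GLMM analysis will model outcome as a curvilinear (quadratic) or exponential function of time", with AIC and BIC deciding between the two. The only reason given is "since PPA is expected to decrease rapidly at first and then level off over time".
- **Slope (Aim 1a).** "Treatment differences in slopes will indicate different rates of decrease in PPA".
- **Level at a chosen time (Aim 1a).** Time may be re-centred to compare the arms at a given assessment. Week 24 is the only example.

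On withdrawal itself, the protocol's Measures section says "we will monitor withdrawal severity at baseline, weekly throughout treatment and at follow-up assessments". Table 2 places the scale at baseline, weeks 1 to 4, quit week (week 5), and then 1, 2, 4, 8, 10, 16 and 24 weeks after quitting. The participant-protection text under Risks says "withdrawal symptoms are usually short-lived, with most symptoms abating within 1-2 weeks".

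The SAP gives withdrawal no time origin, no break at the quit date and no named time point.

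**The concern.** A curve chosen for an outcome that falls and then flattens need not suit one that is probably low while people smoke, rises on quitting and fades within weeks. A quadratic over 29 weeks cannot follow a rise and fall lasting two to three weeks, and an exponential running from baseline cannot peak at all. If the model starts at the quit date instead, an arm with a lower peak has less far to fall, so its slope is flatter. A reader who looks only at the slope could take that for a weaker result.

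Withdrawal is an Aim 2 outcome and a proposed mediator. Aim 3a computes its path a as in Aim 2a, and the Power Analysis describes that path as the mediator's slope over time. A blurred or ambiguous slope would therefore carry into the mediation analysis. This is a trial meant to supply initial effect sizes and to isolate mechanisms.

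**Working it through.** **The plan's own figure.** The Power Analysis (Aim 3) reports power above .95 for a d = .50 moderation of path a. A plain two-mean comparison gives z = 0.5/√(2/40) = 2.24 and power .61 (two-sided .05). Reaching .95 needs a contrast variance of about (2.24/3.605)² = .38 of the simple one. The variance components are not given, so the figure can be neither reproduced nor refuted. It also takes the slope as the right summary, which is the question here.

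**Inputs from the documents.** 80 participants in two arms; withdrawal visits at weeks -5, -4, -3, -2, -1, 0, 1, 2, 4, 8, 10, 16 and 24 relative to quitting (Table 2).

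**Assumptions (not in the documents).** 40 per arm, total SD 1, exchangeable correlation ρ of .4 to .6, two-sided .05, complete data. Placebo withdrawal is 0 before quitting, +1 SD at WK 0 and WK 1, +0.5 at WK 2 and 0 afterwards; DCS halves it. The true arm difference is therefore -0.50, -0.50 and -0.25 at WK 0, 1 and 2, and 0 elsewhere.

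**Method.** Let X hold the curve's time terms, δ the true differences at the visits and V = (1-ρ)I + ρJ. The fitted difference has coefficients (X'V⁻¹X)⁻¹X'V⁻¹δ and variance (2/40)(X'V⁻¹X)⁻¹. Power follows from z = estimate/SE.

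**(a) All 13 visits, one quadratic**

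- Fitted to the noise-free placebo means, the curve reads 0.24 at WK 0 and 0.25 at WK 1, where the truth is 1.0.
- Level at WK 1: -0.13 SD against -0.50, which is 0.127/0.50, about 25%. SE is .152 to .179 and power .13 to .11.
- Level at week 24: power .05 to .07.
- Slope centred at baseline: power .09 to .11. Slope centred at quit: .07 to .08.

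Re-centring only moves along the same wrong curve.

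**(b) Eight visits from WK 0, one curve**

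- Quadratic slope at WK 0: about +0.07 SD per week, power .74 to .89. The arm with less withdrawal declines more slowly.
- Quadratic level at WK 0: -0.44 SD, power .62 to .69.
- Exponential level at WK 0, half-life 1 to 3 weeks: -0.61 to -0.50 SD, power .71 to .83.

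**Different shape.** Let the DCS effect be 0.5 SD at WK 0, halving every 0.5 to 1.0 week, with correlation .3 to .7.

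- All visits: a quadratic recovers 13 to 18% of the WK 0 difference (power .06 to .10), and an exponential from baseline 10 to 17%.
- Post-quit visits: a quadratic recovers 51 to 66% at WK 0, with a positive slope difference (+0.044 to +0.053 SD per week). An exponential recovers 100% at the right rate and 55 to 70% with a 4-week half-life.

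**Named early contrast (first scenario).**

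- Mean difference over WK 0-2: (0.50 + 0.50 + 0.25)/3 = 0.417 SD.
- Residual variance after adjusting for one baseline score: (1+2ρ)/3 - ρ² = .440 at ρ = .4 and .373 at ρ = .6.
- SE = √(2 × variance/40) = .148 and .137, so z = 2.81 and 3.05, and power is .80 to .86.
- Adjusting for all five pre-quit scores gives .93 to .98.

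**Lasting effect.** If DCS lowers withdrawal by 0.5 SD from quitting onward, the all-visits quadratic slope centred at WK 0 or WK 1 has power .97 to 1.00. The early contrast has z = 0.5/.148 = 3.37 to 0.5/.137 = 3.66, power .92 to .96.

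**The case against.** The strongest reply is that Aim 1a offers more than a slope. It allows an arm comparison at any assessment, and Aim 2a imports that too. With post-quit visits centred at WK 0, most of the effect is recovered. On the noise-free post-quit placebo curve the exponential also fits better (residual sum of squares .13 to .23, against .31 for the quadratic), so AIC/BIC might well choose it. The Overview calls the continuous-outcome models only similar to the abstinence model, which leaves room to adapt. All of this stands. What remains is that the plan commits to none of these choices: which visits enter, where time starts, or which time point counts.

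The comparison also favours the early contrast by construction, because the assumed effect sits at exactly the weeks being averaged. The documents give no shape for the DCS effect. The protocol describes DCS as helping extinction to be retained, so a lasting effect is plausible, and the all-visits slope would detect it. That stands, and it limits the claim to a transient effect.

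The peak is inferred, not stated. All participants start the patch at quitting, and the protocol expects it to reduce severity. Table 1 asks for four smoke-free hours before Sessions 3 and 4, so pre-quit scores may not be flat. Complete data is optimistic too, since the SAP's own power work assumes 71% of post-quit assessments. These points change the size of the loss but give no reason why one smooth curve should suit withdrawal.

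Finally, withdrawal is one of five psychological outcomes in a study whose stated goal is feasibility and whether to proceed to Stage II. The consequence is limited, but so is the cost of the change.

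**Conclusion.** The point holds as a weakness of specification with a cheap remedy. If all visits enter one quadratic, an assumed transient reduction of 0.5 SD is estimated at about a quarter of its size, with power about .1. If only post-quit visits enter, the slope alone can show a lower peak as a slower decline, while the early centred contrast recovers -0.44 SD (quadratic) or -0.50 to -0.61 SD (exponential). These figures rest on 40 per arm, correlation .4 to .6, complete data and the assumed peak. The direction was the same under the faster-decaying shape and wider correlation range.

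A reader might infer two stronger things that the documents do not support.

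- **That withdrawal is lost or misread whichever visits are used.** The time-point contrast in Aim 1a contradicts this for post-quit data.
- **That a benefit would be reported with its sign reversed.** A lower peak really does decline more slowly, so the slope estimate is correct. The SAP nowhere equates faster decline with benefit, and for abstinence a slower decrease is the hoped-for result. A false reading would require ignoring the companion level contrast.

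Nor do the documents say that withdrawal peaks at the quit date. That follows from the stated one-to-two-week course and the quit-week design.

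**What to change.** - **Aim 2a model.** Take withdrawal out of the shared rule. Use a multi-level model with visit as a categorical factor, or piecewise with a knot at the quit date, adjusted for the baseline score.
- **Main contrast.** Name the arm difference in mean Minnesota Withdrawal Scale score over WK 0, WK 1 and WK 2. Report the WK 4-24 difference alongside it, so that a lasting effect is visible.
- **Interpretation.** State that a post-quit slope difference in withdrawal will not be read on its own as benefit or harm.
- **Aim 3a.** Take the withdrawal path a within each arm from the same model, as the change from pre-quit to WK 0-2, and state which pre-quit visits define the starting value. Do not use the between-arm contrast as path a, because Aims 3a and 3c estimate and test the pathways separately in each condition.

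The cost is SAP wording, including an exception for withdrawal where the Power Analysis describes path a as a slope. Every visit needed is already in Table 2. The downsides are small: the model has more parameters, and the main withdrawal test concentrates on the early weeks.
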